Institutional Review Board Intervention/Interaction Detailed Protocol

Principal Investigator:	[name], MPH
Project Title:	Addressing diffusion of responsibility and prescribing burden to improve use of diabetes medications
Version Date:	July 18, 2024
Version Name/Number:	Version 14

1. Background and Significance

Type 2 diabetes control in the US is suboptimal, and poor control is tightly linked to morbidity and mortality. For example, one year with a hemoglobin A1c (HbA1c) >7.5% is estimated to equate to a loss of approximately 100 life days.² Thus, disease control is imperative for healthy aging among patients with diabetes. Two newer classes of antidiabetic agents, SLGT2is and GLP-1Ras, improve glycemic control, induce weight loss, reduce the risk of cardiovascular events and renal disease, and decrease all-cause mortality.³⁻⁵ The American Diabetes Association recommends the use of these medication classes for patients with type 2 diabetes and kidney disease, cardiovascular disease, heart failure, or obesity.⁶ Despite this, adoption has been slow.⁷⁻¹⁰ While over 50% of patients with diabetes are eligible, only 1-5% of eligible patients receive one of these drugs.^{1,8,9}

While diabetes is commonly managed by primary care providers, SGLT-2i and GLP-1Ras are indicated for individuals with type 2 diabetes who also have other comorbidities, and so multiple specialists are often involved in this care. This results in significant "diffusion of responsibility," a behavioral concept that refers to the tendency of people (in this context, prescribers) to feel less responsible for individual actions in a setting or system when there are multiple actors and responsibility is unclear.^{11,12,13-15} This behavioral barrier is increasingly recognized in the medical context.¹⁶⁻²¹ In the case of SGLT-2i and GLP-1RA prescribing, diffusion of responsibility across multiple providers may explain the suboptimal prescribing of these medications by primary care providers.

Interventions to address diffusion of responsibility have been evaluated in a few medical and several non- medical contexts and suggest promising approaches. Modeling the desired behavior, assigning responsibility to individuals or smaller groups, highlighting individuals' competence to act, and highlighting the perceived harm of the situation to be addressed all have been shown to be effective.^{17,22-24} Each of these factors can be translated to an intervention designed to address diffusion of responsibility in diabetes prescribing.

Because SGLT-2is and GLP-1Ras are relatively new, prescribing can be complicated. For example, the initial medication choice may not be covered by insurance, which results in the patient or pharmacy communicating with the prescriber's office who then communicates with the insurance company to

resolve the issue. Sometimes the provider will need to prescribe a different medication; other times a prior authorization or "peer to peer" conversation with the insurer is needed. At best, this series of denials and changes to the plan delays the start of the medication, but often it prevents initiation completely. The complexity and work required for this process is burdensome for providers and can deter future prescribing.²⁵ This will be partly addressed through electronic prior authorization, which is beginning to be used in routine practice, but further simplification of the process with administrative support could also promote prescribing.

As with non-health behaviors,¹³ the impact of diffusion of responsibility on prescribing, and the success of interventions to address it, may vary based on the patient, provider, and clinical scenario. If it were possible to predict, using routinely collected data from the EHR, when addressing diffusion of responsibility is sufficient or when additional prescribing support is needed, this would allow for more precise intervention tailoring and allocation of resources.

2. Specific Aims and Objectives

Sodium-glucose cotransporter-2 inhibitors (SLGT-2is) and glucagon-like peptide-1 receptor agonists (GLP-1RAs) are evidence-based medications that reduce morbidity and mortality for individuals with diabetes but remain significantly underused.¹ Diffusion of responsibility in prescribing across multiple providers and a burdensome prescribing process are barriers to their optimal use. To address these issues, we propose the following Aims:

Aim 1: Test the impact of an intervention to target diffusion of responsibility with and without additional reduction in prescribing burden on SGLT-2i and GLP-1RAs prescribing compared to usual care. We will conduct a randomized trial among primary care providers. The primary outcome will be SGLT-2i and GLP-1RA prescribing for patients with poorly controlled type 2 diabetes and a clear indication for one of these medications.

[figure not shown]
Aim 2: Identify characteristics of the patient, provider, and their clinical interaction that are associated with responsiveness to each intervention using routinely collected EHR data. The effectiveness of these interventions may vary based on characteristics of patients, providers, or the clinical scenario. Identification of predictors of responsiveness will help target interventions to those most likely to benefit.

3. General Description of Study Design

This study will be conducted within MGH primary care. As with prior work, we will use the hospital's EHR database, the Epic Enterprise Data Warehouse, to identify patients. Patients will be eligible if they are: adults 18-84 years of age with poorly controlled type 2 diabetes (defined as HbA1c >7.0%) and a compelling indication for an SGLT-2i or GLP-1RA (including cardiovascular disease, kidney disease, heart failure, or obesity), who are not already prescribed one of these therapies. We will exclude individuals with end stage renal disease, dementia, type I diabetes, or an EHR indicator of hospice care. We will also exclude patients who are not on the MGH diabetes registry, because patients who are excluded from the registry typically have a clinical reason for alternative diabetes goals or care plans. All attending MGH PCPs (excluding those involved in the design or delivery of the intervention) will be included in the trial. Eligible PCPs will be randomized to one of three arms: (1) intervention to address diffusion of responsibility, (2) intervention to address diffusion of responsibility plus additional simplification of the prescribing process, and (3) usual care. Providers randomized to arm 1, the intervention to address diffusion of responsibility will receive an email from a peer offering encouragement and support in

prescribing SGLT-2is and GLP-1RAs that includes specific components designed to reduce diffusion of responsibility. The email will also offer for direct support from the peer. Providers randomized to arm 2, the intervention addressing diffusion of responsibility and simplifying the prescribing process will receive the same contact addressing diffusion of responsibility as in arm 1, but they will additionally have access to an experienced administrative team for diabetes medication insurance authorization support. The primary outcome will be the rate of prescriptions for SGLT-2is and GLP-1RAs among eligible patients.

3.1 Study Schema

4. Subject Selection

This study will be conducted within MGH primary care, which consists of over 190 attending PCPs caring for more than 13,300 patients with diabetes, approximately 25% of whom have an HbA1c above goal. There will be two participant populations included in the study. First, we expect to enroll 191 providers to receive the intervention. Second, although they will not be receiving the intervention, we expect to accrue 1468 patients whose information will be used to determine study outcomes. Details for waiver of informed consent and waiver of HIPAA authorization are detailed below.

4.1 Inclusion/Exclusion Criteria

We will include attending primary care physicians meeting the following criteria:

• Practicing in primary care at Massachusetts General Hospital

Providers will be excluded if they are involved in the design or conduct of this study (e.g. Drs. [name] and [name], and the peer PCPs delivering the study intervention).

We will accrue patients as part of study intervention delivery and outcome collection. Patient inclusion criteria are:

- 18-84 years of age
- HbA1c >7.0% and a compelling indication for an SGLT-2i or GLP-1RA (including cardiovascular disease, kidney disease, heart failure, or obesity)
- Not already prescribed an SGLT-2i or GLP-1RA at the time of the intervention

We will exclude individuals with end stage renal disease, dementia, type I diabetes, or an EHR indicator of hospice care. We will also exclude patients who are not on the MGH diabetes registry, because patients who are excluded from the registry typically have a clinical reason for alternative diabetes goals or care plans.

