4.2 Patient Identification

Patients will not directly receive intervention, but their clinical parameters will be used to identify upcoming visits with potential opportunities for prescription of an SGLT-2i or GLP-1RA medication. As with prior work, we will use the hospital's EHR database, the Epic Enterprise Data Warehouse, to identify eligible patients.

4.3 Recruitment Procedures

We will use the hospital's EHR database, the Epic Enterprise Data Warehouse, to identify eligible patients.

As with similar minimal-risk quality-improvement studies that we have performed that involve the use of routine clinical tools such as patient portals or physician reminders, informed consent will not be sought in this study, and we request a waiver of informed consent. The nature of this intervention involves the use of messages delivered via email and in-basket (using information already available to providers and delivered via a similar infrastructure they use during regular clinical care). Obtaining written informed consent would also not produce generalizable knowledge about the effectiveness of the intervention, a foundational aspect of pragmatic clinical trial principles. With an approved waiver of informed consent for provider participation, all attending MGH primary care providers will be directly included in the study.

While providers and patients will not be consented into the study, an organization-wide announcement will be circulated across MGH Primary Care Practices to inform providers of the launch of this support for improved prescribing for adults with sub-optimally controlled diabetes.

Providers will be able to request unenrollment from the study at any time by replying to the intervention email. However, because the intervention includes only emails and in-basket messages that support prescribing, we anticipate that retention rates in the study will be very high. Study staff and data analysts will track any physician turnover in the study as they have done in prior work, and though minimal physician turnover is expected, we expect any turnover to bias the trial results towards the null.

5. Subject Enrollment

We will use the hospital's EHR database, the Epic Enterprise Data Warehouse, to identify eligible patients.

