6.2.1 Aim 1 Design

In Aim 1 of the study, we will conduct a 3-arm randomized controlled trial to compare the effectiveness of two interventions compared to usual care on SGLT-2i and GLP-1RA prescribing. We will include Massachusetts General Hospital Attending Primary Care Providers. Interventions will be linked to upcoming visits with patient aged 18-84 years with poorly controlled type 2 diabetes (HbA1c >7.0%) and a compelling indication for an SGLT-2i or GLP-1RA (including cardiovascular disease, kidney disease, heart failure, or obesity), who are not already prescribed one of these therapies. We will exclude patients with a documented allergy to both medication classes, end stage renal disease, dementia, type I diabetes, an EHR indicator of hospice care and those who are excluded from the MGH diabetes registry.

Providers will be randomized equally to one of three arms: (1) intervention to address diffusion of responsibility, (2) intervention to address diffusion of responsibility plus additional simplification of the prescribing process, and (3) usual care. The intervention period will continue for 6 months.

Providers randomized to arm 1, an intervention to address diffusion of responsibility, will receive an email from a peer offering encouragement and support in prescribing SGLT-2is and GLP-1RAs that includes specific components designed to reduce diffusion of responsibility. Specifically, these elements are adapted from interventions that mitigate diffusion of responsibility in other contexts, including (1) assigning a responsibility to individuals or smaller groups, (2) increased perceived harm of the situation to be addressed (3) highlighting competence to act, and (4) modeling the desired behavior. The email will also contain an offer for direct support from the peer. Four MGH primary care physicians will administer the intervention. The email will be sent by the study team on their behalf and will contain a personalized subject line and/or text to increase the likelihood of opening and reading (see Study Interventions Document]).

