As in Arm 1, the initial email will be accompanied the additional personal outreach 3-4 and 6 months after the start of the intervention, and up to 3 follow-up Epic in-basket messages per provider, per week, but in Arm 2 the follow-up messages will also include information on the covered medication choice(s) for each patient how to access additional CAU support. Providers will be invited to reply directly that in-basket message to request assistance with prior authorization if needed. This team will then follow up with the pharmacy to determine coverage, communicate with clinic medical assistants, complete prior authorizations, determine alternative covered options, and track the process, as needed in each case. From the primary care doctor's perspective, this will be a markedly smoother process than current prescribing. If providers assigned to this arm reach out with questions regarding insurance coverage or prior authorization for an eligible patient that does not have an upcoming visit, the CAU staff will deliver the intervention with covered medication choice(s) to the provider at that time. If the patient later has an upcoming visit and has still not been prescribed the medication, the CAU staff will deliver the intervention again in the typical time frame (3 business days prior to the visit). Interventions regarding a single patient will be capped at no more than 3, including any interventions not associated with visits but delivered after PCP request. If providers assigned to this arm reach out with questions regarding ineligible patients, PCP peers will provide them with the same generic resources given in arm 1 that are currently available in routine care.

Prior to enrollment of providers into this trial, the CAU will pilot test Epic in-basket versus email workflow to determine the most efficient workflow. This pilot testing will be done with panels of those PCPs who are not included in the study due involvement in the study (i.e., PI and peer providers).

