All providers will receive the second personal outreach 6 months after the start of the intervention. The outreach will consist of an email notifying them that the study is ending and inviting them to participate in a brief survey. The fact sheet for survey participation will be attached to the email. The survey will be accessed through a unique link to a secure REDCap survey embedded into the email. REDCap is a secure, HIPAA-compliant web-based platform hosted on Mass General Brigham servers. Providers who click on the link to the survey will be met with a landing page that displays the fact sheet describing the study. They will then be able to click a button to indicate that they agree to participate. Providers who select that they agree will then proceed to the rest of the survey. All providers will be allows to respond. Participants will be offered remuneration in the form of a \$25.00 Amazon gift card for completing the survey. An email will be sent to the physician upon completion of the survey containing the claim code they will use to access their gift card. In addition, an electronic copy of the prescribing chart given to intervention arms, providers will also receive a list of the patients who remain eligible for one of these medications but who have not had a visit during the study intervention period. Providers will then have

the option to ask their administrative staff to schedule visits with these patients, consider prescribing asynchronously, or otherwise generate a plan of care. The survey to intervention providers will capture opinions on the interventions, mechanisms behind diffusion of responsibility in prescribing these medications, and thoughts about potential helpful interventions moving forward. Providers in the control arm will only be asked the questions about mechanisms behind diffusion of responsibility in prescribing these medications and thoughts about potential helpful interventions moving forward. All providers who have not completed the survey within 2-3 weeks of receiving the email invitation will receive a follow-up email asking them again to participate in the survey.

Providers randomized to arm 3, usual care, will not receive any outreach outside of the end of study notification and survey.

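### The check for prior prescribing is anchored to a time of intervention that falls after randomisation and does not exist in usual care, so early successes can drop out of the primary denominator

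*Combined protocol and SAP*

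**What the plan says.** Section 5.2 randomises PCPs 1:1:1 to the three arms. Section 4.1 then says of patients: "We will accrue patients as part of study intervention delivery and outcome collection". One inclusion criterion there is "Not already prescribed an SGLT-2i or GLP-1RA at the time of the intervention".

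Section 4.2 says that patients' clinical data will be used "to identify upcoming visits with potential opportunities for prescription of an SGLT-2i or GLP-1RA medication", and section 6.2.1 adds: "Interventions will be linked to upcoming visits with patient aged 18-84 years". In section 6.2.1 the PCP first gets a launch email. In-basket messages about individual patients with upcoming visits follow.

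In Arm 2 only, if a PCP asks about coverage or prior authorisation "for an eligible patient that does not have an upcoming visit, the CAU staff will deliver the intervention" at that point. A further message goes out before a later visit if the patient has still not been prescribed. In Arm 1, a PCP's question brings a reply from the peer and, where useful, resources already available in routine care. Usual-care PCPs "will not receive any outreach outside of the end of study notification and survey".

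Section 3 defines the endpoint: "The primary outcome will be the rate of prescriptions for SGLT-2is and GLP-1RAs among eligible patients". Section 9.1.1 names generalized estimating equations but gives no analysis population, index date or visit rule.

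**The concern.** In a provider-randomised trial, the arms are comparable only if patients are counted by a rule that the allocated arm cannot influence. Here an eligibility criterion is checked at a moment defined by the intervention. In the intervention arms that moment can come after the PCP has already been exposed. In usual care it is undefined.

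The launch email addresses the PCP's prescribing in general, before any patient-level message. If it works, some patients will be started before their visit comes up. Checked at the visit-linked message, those patients fail the criterion and are not counted, although they are what the intervention set out to achieve. In Arm 2 a patient started after a coverage request, with no visit scheduled, can be lost in the same way. A regression on the accrued patients cannot restore patients who were never accrued. Each intervention's contrast with usual care is exposed. So is Arm 2 against Arm 1, because the request route exists in only one of them.

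**Working it through.** **Which readings the text allows**

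- *All patients meeting the data-warehouse criteria.* Sections 3 and 6.2 define the outcome among eligible patients. The end-of-study list in section 6.2.1 treats patients with no visit in the period as still eligible. Under this reading, with prior prescribing checked at study start, nobody drops out.
- *Visit-linked patients.* Sections 4.2 and 6.2.1 tie identification and delivery to upcoming visits, and the chart-review paragraph of section 6.2.1 equates the primary outcome with a prescription at the target visit. If prior prescribing is checked at that point, early starters drop out.
- *The phrase in section 4.1* does not decide between them. Elsewhere the protocol uses the start of the intervention as a study-level date, but section 6.2.1 also speaks of interventions regarding a single patient.

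**Inputs from section 9.2**

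Control rate 30%; difference 11 points, so 41% under intervention; ICC 0.07; 7 patients per provider; type I error 5% (sidedness not stated, taken as two-sided); power 80%.

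The provider count reproduces. With continuity correction, 30% versus 41% needs 314 patients per arm. The design effect is 1 + (7 - 1) × 0.07 = 1.42. Then 314 × 1.42 = 445.9 per arm, 1337.6 over three arms, and 1337.6 / 7 = 191.1 against the stated 191. (191 × 7 = 1337, not 1468; that is a separate matter to reconcile.)

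**Illustration on the visit-linked reading**

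Per 100 patients, let E be the number started before the check. The observed rate is (prescribed - E) / (100 - E). The early shares below are assumed; the documents give none. The same visit-time check is assumed to be imposed on usual care.

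| Assumed early share | Usual care | Intervention | Difference seen |
|---|---|---|---|
| 20% of all prescriptions | E = 6: 24/94 = 25.5% | E = 8.2: 32.8/91.8 = 35.7% | 10.2 points |
| 20% of background, 50% of the extra 11 | E = 6: 24/94 = 25.5% | E = 6 + 5.5 = 11.5: 29.5/88.5 = 33.3% | 7.8 points |

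The shrinkage comes from extra prescriptions that arrive early. If 20% of background but none of the extra did, the difference would be 35/94 - 24/94 = 11.7 points.

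**The case against.** The strongest reply is that the denominator is already defined without reference to arm: eligible patients, identified from the data warehouse. The accrual sentence names outcome collection as well as delivery, and usual-care patients can enter only through the former. The time of the intervention may simply mean the study-level start. These points stand as far as they go. They show that a sound reading exists, not that the plan adopts it. Eligibility itself contains the ambiguous check, the visit-linked passages point the other way, and no section fixes a date.

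A reader might go further and infer that Arm 2 requests bring additional, nearly certain prescriptions into its denominator and so inflate its rate. The documents do not support that. The request concerns a patient already called eligible, and no section says that it adds anyone to the analysis. If all eligible patients count, that patient is already in. If a target visit is needed, a patient with a request and no visit is out. If only messaged patients counted, usual care would have no denominator at all. Inflation needs a mixed rule that appears nowhere.

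It is also fair to say that the attenuation figures rest on assumed shares. They show what could happen and are not estimates.

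**Conclusion.** The concern holds in conditional form. The plan states an eligibility check whose timing depends on the intervention, can follow randomisation, and cannot be applied as written in usual care. On the visit-linked reading this can remove early successes from the intervention arms and, in Arm 2, also patients started after a request. In the two illustrated cases, a true 11-point difference would appear as 10.2 or 7.8 points. That rests on the assumed early shares and on a matching check in usual care, and the direction depends on extra prescriptions coming early.

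The documents do not establish that the denominators will in fact differ by arm, only that the written rule leaves this open. They give no basis for claiming that Arm 2 is inflated. The change is worth making because it replaces a stated rule that risks bias in the primary comparison and does more than add detail.

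**What to change.** In sections 4.1 and 6.2:

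- Define the primary denominator by one data-warehouse query, run identically for all randomised PCPs in all three arms.
- Replace the time-of-intervention anchor. Fix prior-prescription status and PCP attribution at a common index date: intervention start or, for patients who qualify later, the date they first meet the data-warehouse criteria.
- Count patients whether or not a message was sent or a request made.
- If a visit is required, apply the same scheduled-visit trigger to usual care, and do not exclude patients first prescribed between the index date and that visit.

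The cost is protocol wording and one query; delivery of the intervention is unchanged. The small downside is that some counted patients will have had no message, and the patient total may differ from 1468.
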